### Revision of Exclusion Criterion #13

Exclusion Criterion #13 was revised to exclude subjects with prior treatment with 3 biologics as opposed to 2 biologics.

The rationale is based on the expectation of responsiveness to GED 0301 (with a different mechanism of action than biologic therapy) in terms of clinical and endoscopic benefit, which is expected to be substantively similar in patients having been exposed to either 2 or 3 biologics. The intention, therefore, is to study a broader group of patients with prior biologic exposure. The target of 65% of the subjects in this trial to be naive to prior biologic therapy is unchanged.

Revised Sections:

- Protocol Summary, Study Population
- Section 4.3, Exclusion Criterion # 13

**The amendment also includes several other minor clarifications and corrections:**

- Update of Inclusion Criterion #9 to allow subjects who are at risk for colorectal cancer to have a colonoscopy within 2 years of the Baseline Visit.
- Update of Exclusion Criterion #22 to clarify that subjects treated with intravenous antibiotics for clinically significant infection prior to the Screening Visit, are excluded from the study. Subjects are permitted oral antibiotics to treat infection prior to the study.
- Update of Exclusion Criterion #24 to clarify that subjects with colonic polyps are permitted in the study.
- Clarification of subjects who require a Follow-up Visit. Subjects who escape into the Long-term Active-treatment Study will have the Early Termination Visit but not the Follow-up Visit.
- Correction of footnotes in Table 3.
- Correction to Table 3 (Week 52 Visit). Investigational product is not dispensed at Week 52.
- Correction to Table 3 (Early Termination Visit). Visit Number is Visit 16.
- Correction to Section 6.6.4, Ileocolonoscopy. Biopsies are not being done in this study. The word “biopsies” is deleted from this section.
- Correction of formatting in Section 6.2.(dispensing of IP).
- Correction to [REDACTED]
- Correction to Appendix H, Definition of CD Treatment Failure and Intolerance

## 1. LIST OF ABBREVIATIONS

**Table 1: Abbreviations and Specialist Terms**

Abbreviation	Meaning
AE	Adverse event
ALT	Alternating
ANCOVA	Analysis of covariance
APTT	Activated partial thromboplastin time
ATC	Anatomical Therapeutic Chemical
ATC2	Anatomical Therapeutic Chemical: Therapeutic (Level 2)
AZA	Azathioprine
BMI	Body mass index
BUN	Blood urea nitrogen
CBC	Complete blood count
CD	Crohn's Disease
CDAI	Crohn's Disease Activity Index
CI	Confidence interval
CMH	Cochran-Mantel-Haenszel
DAO	Data as observed
ECG	Electrocardiograms
eCRF	Electronic case report form
ET	Early Termination

Abbreviation	Meaning
IP	Investigational product
ITT	Intent-to-treat
IWRS	Interactive Web Response System
LDH	Lactic dehydrogenase
LOCF	Last observation carried forward
LS	Least-squares
MCH	Mean corpuscular hemoglobin
MCHC	Mean corpuscular hemoglobin concentration
MCV	Mean corpuscular volume
MedDRA	Medical Dictionary for Regulatory Activities
MNAR	Missing not at random
6-MP	6-mercaptopurine
MTX	Methotrexate
NRI	Nonresponder imputation
PP	Per-protocol
PT	Preferred term

Abbreviation	Meaning
Q1	25 th percentile
Q3	75 th percentile
QD	Once Daily
RBC	Red blood cell
SAP	Statistical analysis plan
SD	Standard deviation
SE	Standard error
SES-CD	Simple Endoscopic Score for Crohn's Disease
SGOT	Serum glutamic-oxaloacetic transaminase
SGPT	serum glutamic-pyruvic transaminase
SOC	System organ class
TEAE	Treatment-emergent adverse event
TNF- $\alpha$	Tumor necrosis factor-alpha
ULN	Upper limit of normal
VAS	Visual analog scale
WBC	White blood cell
WHODD	World Health Organization Drug Dictionary

## 2. INTRODUCTION

This statistical analysis plan (SAP) describes the analyses and data presentations for Celgene's protocol GED-0301-CD-002 "A Phase 3, Randomized, Double-blind, Placebo-controlled, Multicenter Study to Investigate the Efficacy and Safety of Mongersen (GED-0301) for the Treatment of Subjects with Active Crohn's Disease" as amended on 15 Aug 2017. It contains definitions of analysis populations, derived variables and statistical methods for the analysis of efficacy and safety.

The study was terminated early by Celgene following an October 2017 recommendation of the Data Monitoring Committee. As such, changes are made to some protocol-specified analyses; these changes are described in relevant sections and summarized in Section 16.

In this SAP, GED-0301 160 mg once daily (QD) and GED-0301 40 mg QD are referred to as GED 160 and GED 40, respectively. Subjects will be randomized to receive 1 of 3 GED-0301 treatment regimens or placebo during the study. For the first 12 weeks of the study, each GED-0301 treatment regimen will consist of GED 160. These 12 weeks will be followed by either 1) placebo QD for 4 weeks followed by alternating (ALT) GED 160 for 4 weeks and placebo QD for 4 weeks until the end of the study; 2) placebo QD for 4 weeks followed by alternating GED 40 for 4 weeks and placebo QD for 4 weeks until the end of the study; or 3) continuous GED 40 until the end of the study. These 3 GED-0301 treatment regimens will be referred to as GED 160/GED 160 4 WK ALT, GED 160/GED 40 4 WK ALT, and GED 160/GED 40, respectively. Investigational product (IP) refers to placebo, GED 160, or GED 40.

## 4. INVESTIGATIONAL PLAN

### 4.1. Overall Study Design and Plan

This is a Phase 3, randomized, double-blind, placebo-controlled, multicenter study to evaluate the efficacy and safety of 3 treatment regimens of oral GED-0301 versus placebo in subjects with active CD (defined by a CDAI score  $\geq 220$  and  $\leq 450$  and a total SES-CD  $\geq 6$  at screening, or the ileum segmental SES-CD  $\geq 4$  at screening). Approximately 1064 subjects will be randomized in a 1:1:1:1 ratio (266 subjects per GED-0301 arm [total 798]; 266 subjects in the placebo arm) to receive 1 of 3 double-blind, oral GED-0301 treatment regimens, or identically appearing placebo once daily (QD) for 52 weeks. The total number of subjects with a total SES-CD score  $\geq 6$  is targeted to comprise approximately 80% of the study population.

Treatment assignment at baseline (Week 0/Visit 2) will be stratified via an Interactive Web Response System (IWRS) based on concomitant use of corticosteroids (yes/no); concomitant use of immunosuppressants (eg, azathioprine [AZA], 6-mercaptopurine [6-MP], or methotrexate [MTX]) (yes/no), and previous exposure to biologics (ie, infliximab, adalimumab, certolizumab or vedolizumab) (yes/no). The total number of subjects with previous exposure to biologics is targeted to comprise approximately 35% of the study population.

Subjects will receive double-blind, oral GED-0301 or identically appearing placebo QD as follows:

- GED-0301 160 mg QD for 12 weeks; followed by placebo QD for 4 weeks; followed by alternating GED-0301 160 mg QD for 4 weeks and placebo QD for 4 weeks, until the Week 52 Visit;
- GED-0301 160 mg QD for 12 weeks; followed by placebo QD for 4 weeks; followed by alternating GED-0301 40 mg QD for 4 weeks and placebo QD for 4 weeks, until the Week 52 Visit;
- GED-0301 160 mg QD for 12 weeks; followed by continuous GED-0301 40 mg QD, until the Week 52 Visit;
- Placebo QD until the Week 52 Visit.

Subjects who complete the GED-0301-CD-002 study at the Week 52 Visit may enter the Long-term Active-treatment Study (GED-0301-CD-004). Subjects who meet the criteria for early escape beginning at the Week 12 Visit and thereafter until the Week 52 Visit, may (a) continue in the study at the discretion of the Investigator based on the totality of clinical data, (b) enter the Long-term Active-treatment Study (GED-0301-CD-004), or (c) discontinue the study.

The criteria for early escape are defined as

Subjects may discontinue the study at any time. Subjects who discontinue from the study at Week 12 (either because they meet the early escape criteria or for any other reason), will complete the Week 12 Visit. Subjects who prematurely discontinue from the study at any other

[figure not shown]
time prior to the Week 52 Visit, including subjects who early escape into the Long-term Active-treatment Study, will complete the Early Termination (ET) Visit. The ET Visit should be scheduled as soon as possible after the last dose of IP.

Subjects who complete the Week 52 Visit, as well as subjects who prematurely discontinue from the study, will have a 4-week Follow-up Visit. If the ET Visit occurs 28 days or more after the last dose of IP, then the Follow-up Visit is not required.

Subjects entering the Long-term Extension Study will not have the Follow-up Visit.

A schematic of the study design is in [Figure 1](#).

**Figure 1 Overall Study Design**

## 4.2. Study Endpoints

**Table 3: Protocol-specified Endpoints**

Endpoint	Name	Description	Timeframe
Primary	Efficacy (Clinical remission)	The proportion of subjects achieving clinical remission, defined as a CDAI score < 150, at Week 12	Week 12
Secondary	Efficacy	The proportion of subjects achieving clinical remission, defined as a CDAI score < 150, at Week 52	Week 52

**Table 3: Protocol-specified Endpoints (Continued)**

Endpoint	Name	Description	Timeframe
	Efficacy	The proportion of subjects with endoscopic response-50 (ER-50), defined as a reduction of at least 50% in the SES-CD compared with baseline, at Week 52	Week 52
	Efficacy	The proportion of subjects who have a clinical response, defined as a decrease from baseline in CDAI $\geq$ 100 points, at Week 12	Week 12
	Efficacy	The proportion of subjects who achieve corticosteroid-free clinical remission (CDAI <150) at Week 52 among subjects receiving oral corticosteroids for CD at baseline	Week 52
	Efficacy	The proportion of subjects achieving sustained clinical remission, defined as a CDAI score < 150 at both Week 12 and Week 52	Week 12 and Week 52
	Efficacy	The proportion of subjects with endoscopic response-25 (ER-25), defined as a reduction of at least 25% from baseline in SES-CD, at Week 12	Week 12
	Efficacy	The proportion of subjects with endoscopic remission, defined as SES-CD $\leq$ 2, at Week 52	Week 52
	Safety	Type, frequency, severity, seriousness, and relationship of AEs to IP	Through Week 52
	Safety	Number of subjects who discontinue IP due to any AE	Through Week 52
	Safety	Clinically significant changes in vital signs, ECGs, and/or laboratory findings	Through Week 52

**Table 3: Protocol-specified Endpoints (Continued)**

Endpoint	Name	Description	Timeframe

AE = adverse event; CD = Crohn's disease; CDAI = Crohn's Disease Activity Index; ECG = electrocardiogram; ; IP = investigational product; SES-CD = Simple Endoscopic Score for Crohn's disease

- GED-0301 160 mg QD for 12 weeks; followed by placebo QD for 4 weeks; followed by alternating GED-0301 160 mg QD for 4 weeks and placebo QD for 4 weeks, until the Week 52 Visit
- GED-0301 160 mg QD for 12 weeks; followed by placebo QD for 4 weeks; followed by alternating GED-0301 40 mg QD for 4 weeks and placebo QD for 4 weeks, until the Week 52 Visit
- GED-0301 160 mg QD for 12 weeks; followed by continuous GED-0301 40 mg QD, until the Week 52 Visit
- Placebo QD until the Week 52 Visit.

Treatment assignment at baseline (Week 0/Visit 2) will be stratified via an IWRS based on concomitant use of corticosteroids (yes/no); concomitant use of immunosuppressants (eg, azathioprine [AZA], 6-mercaptopurine [6-MP], or methotrexate [MTX]) (yes/no), and previous exposure to biologics (ie, infliximab, adalimumab, certolizumab or vedolizumab) (yes/no). The total number of subjects with previous exposure to biologics is targeted to comprise approximately 35% of the study population.

#### 4.4. Sample Size Determination and Power Considerations

With a total of approximately 1064 subjects and a randomization ratio of 1:1:1:1, this study will randomize approximately 266 subjects into each of the three GED-0301 treatment groups and the placebo group. For the efficacy analyses of the first 12 weeks of the study, the three GED-0301 treatment groups will be pooled, due to the same treatment of GED-0301 160 mg QD received during the first 12 weeks, and the treatment comparisons will be made between GED-0301 160 mg QD (approximately 798 subjects) and placebo. For the efficacy analyses beyond Week 12, the treatment comparisons will be made between each of the three GED-0301 treatment groups and placebo. The study sample size is driven by the comparison of each of the three GED-0301 treatment groups with placebo with respect to the proportion of subjects with ER-50 at Week 52. The sample size and power calculations (not accounting for multiplicity adjustment) at a 2-sided significance level of 0.05 are given in [Table 5](#).

**Table 5: Sample Size and Power Calculations**

Endpoint	Assumptions	Sample Size per Group	Power a
Clinical remission (CDAI score < 150) at Week 12	Placebo = 22% GED-0301 160 mg QD = 36%	Placebo = 266 GED-0301 160 mg QD = 798	99%
Clinical remission (CDAI score < 150) at Week 52	Placebo = 22% GED-0301 160 mg QD = 36%	Placebo = 266 Any GED-0301 group = 266	95%
ER-50 at Week 52	Placebo = 10% Any GED-0301 group = 20%	Placebo = 266 Any GED-0301 group = 266	90%

CDAI = Crohn's Disease Activity Index; ER-50 = endoscopic response defined as a reduction of at least 50% in the SES-CD; QD = once daily; SES-CD = Simple Endoscopic Score for Crohn's Disease.

a All power calculations do not account for multiplicity adjustment and are based on a 2-group chi-square test at a 2-sided significance level of 0.05, using EastTM 6.3.

CELGENE PROPRIETARY INFORMATION

## 5. GENERAL STATISTICAL CONSIDERATIONS

### 5.1. Reporting Conventions

The following reporting conventions apply generally to tables, listings, and figures:

- Stratified analyses will use the randomization stratification factors (concomitant use of corticosteroids, concomitant use of immunosuppressants, and previous exposure to biologics), unless otherwise specified.

- Efficacy analyses will be presented by GED-0301 treatment regimen and placebo (the efficacy analyses of the first 12 weeks will additionally include a total group combining all 3 GED-0301 treatment regimens), and safety analyses will be presented by GED-0301 treatment regimen, placebo, and a total group combining all 3 GED-0301 treatment regimens.

- Confidence intervals (CIs) will be presented as 2-sided 95% CIs.
- Summary statistics will consist of the number and percentage of subjects in each category for discrete variables, and the sample size, mean, standard deviation (SD), median, minimum, 25th percentile (Q1), 75th percentile (Q3), and maximum for continuous variables.

- Change from baseline is calculated as the post-baseline value minus the baseline value.

- All laboratory data will be reported using standard international units.

[REDACTED]

## 5.2. Time Points

[REDACTED]

### 5.2.2. Screening and Baseline Definitions

[REDACTED]

Unless otherwise specified, the baseline value is defined as the last assessment on or before the date of the first dose of IP in the study. [REDACTED]

### 5.3. Analysis Populations

#### 5.3.1. Intent-to-treat Population

The intent-to-treat (ITT) population will be the primary population for the efficacy analysis. The ITT population is defined to include all subjects who are randomized and receive at least 1 dose of IP.

Due to the early termination of the study, for binary efficacy endpoints, the denominator at the time point under consideration will include subjects who have either completed that time point

or discontinued at any time due to reasons other than “study terminated by sponsor”, instead of all subjects included in the ITT population (Section 11.2.2.1).

Subjects will be included in the treatment group to which they were randomized for the efficacy analysis using the ITT population.

#### 5.3.3. Safety Population

The analysis of safety data in this study will be based on the safety population, which will consist of all subjects who are randomized and receive at least 1 dose of IP.

At least 1 post-baseline assessment is required for inclusion in the analysis of each specific laboratory, vital sign, weight, or ECG parameter. To assess the change from baseline, a baseline assessment is also required.

Subjects will be included in the treatment group corresponding to the IP they actually received for the analysis using the safety population.

## 6. SUBJECT DISPOSITION

The number of subjects screened, the numbers and percentages of subjects randomized and not randomized, and the numbers and percentages of the eligibility criteria failed will be summarized based on all subjects screened.

The number and percentage of subjects included in the analysis populations will be summarized based on all subjects randomized.

Subject disposition (entered, completed, discontinued, along with the primary reason for discontinuation) will be summarized for

- Double-blind Treatment Period (based on all subjects randomized): Weeks 0-12, Weeks 12-52, and Weeks 0-52
- Follow-up Period (based on all subjects who enter the Follow-up Period): Weeks 0-12, Weeks 12-52, and Weeks 0-52

[Redacted content]

[Redacted]	[Redacted]	[Redacted]	[Redacted]	[Redacted]
[Redacted]	[Redacted]	[Redacted]	[Redacted]	[Redacted]
[Redacted]	[Redacted]	[Redacted]	[Redacted]	[Redacted]

A listing of discontinued subjects with reason for discontinuation will be provided.

The number and percentage of subjects by region, country, and site will be provided based on all subjects randomized.

## 7. **PROTOCOL DEVIATIONS/VIOLATIONS**

Protocol violations and deviations will be summarized for the screening period, Weeks 0-12 and the entire study using the ITT population, and for Weeks 12-52 for subjects who complete Week 12/Visit 5.

A listing of all protocol violations and deviations in the study will be provided.

CELGENE PROPRIETARY INFORMATION

## 8. DEMOGRAPHICS AND BASELINE CHARACTERISTICS

Demographics and baseline characteristics will be summarized descriptively based on the ITT population. The comparability of the treatment groups for each relevant characteristic will be assessed descriptively in table format; no statistical hypothesis tests will be performed on these characteristics. Subject data listings will be provided.

### 8.1. Demographics and Baseline Characteristics

The following characteristics will be summarized as continuous variables:

- Age (years)
- Baseline body weight (kg)
- Baseline body mass index (BMI = weight (kg)/[height(m)]; kg/m^2)

The following characteristics will be summarized as categorical variables:

- Age (< 65, ≥ 65 years; < 40, 40 – < 65, 65 – < 75, ≥ 75 years)
- Sex (Male, Female)
- Race (American Indian or Alaska Native, Asian, Black or African American, Native Hawaiian or Other Pacific Islander, White, Not Collected or Reported, Other)
- Ethnicity (Hispanic or Latino, not Hispanic or Latino, Unknown, Not Reported)
- Region (North America, Western Europe, Eastern Europe, Asia Pacific)
- Baseline body weight (< 55, 55 – < 70, 70 – < 85, 85 – < 100, ≥ 100 kg)
- Baseline BMI (< 18.5, 18.5 – < 25, 25 – < 30, 30 – < 35, 35 – < 40, and ≥ 40 kg/m^2)
- Alcoholic beverages (yes [ $< 1$  drink per week, 1 – 14 drinks per week,  $> 14$  drinks per week], no)
- Tobacco history (never smoked, past smoker, current smoker, passive smoker, smokeless tobacco user)

Age will be calculated as (date of informed consent – date of birth + 1) / 365.25 when the full date of birth is collected; otherwise, the age recorded will be used.

### 8.2. Baseline Disease Characteristics

The following baseline disease characteristics will be summarized as continuous variables:

- Baseline CDAI score
- Baseline SES-CD score (central read)

- Baseline CDAI score ( $\leq 300$ ,  $> 300$ ;  $< 220$ ,  $220 - < 270$ ,  $270 - < 330$ ,  $330 - < 390$ ,  $390 - \leq 450$ ,  $> 450$ )
- Baseline SES-CD (central read;  $< 6$ ,  $6 - 12$ ,  $> 12$ )

### 8.3. Medical History

Medical history will be coded according to the Medical Dictionary for Regulatory Activities (MedDRA), and summarized based on the ITT population by system organ class (SOC) and preferred term (PT), with SOCs sorted in alphabetical order and PTs within each SOC in descending order of frequency, and by PT only in descending order of frequency.

### 8.4. Prior Medications/Procedures

Prior medications are defined as medications with a start date before the date of the first dose of IP in the study (whether or not the end date is before the date of the first dose of IP). Prior medications that continue on or after the date of the first dose of IP will be also reported as concomitant medications. The Anatomical Therapeutic Chemical (ATC) coding scheme of the World Health Organization Drug Dictionary (WHODD) will be used to group medications into relevant categories. Prior medications will be summarized based on the ITT population by ATC2 level and standardized medication name, with ATC2 levels and standardized medication names within each ATC2 level sorted in descending order of frequency.

Prior procedures are similarly defined. Prior procedures will be coded according to the MedDRA, and summarized based on the ITT population by SOC and PT, with SOCs sorted in alphabetical order and PTs within each SOC in descending order of frequency.

## 9. EXTENT OF EXPOSURE TO INVESTIGATIONAL PRODUCT

### 9.1. Treatment Duration

Treatment duration will be summarized for Weeks 0-12 and Weeks 0-52 using the safety population, and for Weeks 12-52 for subjects who receive at least 1 dose of IP after Week 12/Visit 5

Treatment duration will be summarized as a continuous variable, and as a categorical variable with the following exposure intervals:

- Weeks 0-12:  $\leq 4$ ,  $> 4 - 8$ ,  $> 8$  weeks
- Weeks 12-52:  $\leq 8$ ,  $> 8 - 16$ ,  $> 16 - 24$ ,  $> 24 - 32$ ,  $> 32$  weeks (intervals denote the number of weeks relative to the date of the first dose of IP in Weeks 12-52 as defined above)
- Weeks 0-52:  $\leq 4$ ,  $> 4 - 8$ ,  $> 8 - 12$ ,  $> 12 - 20$ ,  $> 20 - 28$ ,  $> 28 - 36$ ,  $> 36 - 44$ ,  $> 44$  weeks

A subject data listing of study drug records will be provided.

### 9.2. Treatment Compliance

As part of the routine recording of the amount of IP taken by each subject, the numbers of tablets dispensed and returned will be recorded at each visit (except the screening and follow-up visits). These records will be used to calculate treatment compliance. Treatment compliance will be summarized for Weeks 0-12 and Weeks 0-52 using the ITT population, and for Weeks 12-52 for subjects who receive at least 1 dose of IP after Week 12/Visit 5

Treatment compliance rate will be summarized as a continuous variable, and as a categorical variable with the following categories:  $< 75\%$ ,  $75\% - 120\%$ , and  $> 120\%$ .

A subject data listing of drug accountability records will be provided.

**9.3. Overdose**

A subject data listing of overdose records will be provided.

[figure not shown]
CELGENE PROPRIETARY INFORMATION

## **10. CONCOMITANT MEDICATIONS AND PROCEDURES**

Concomitant medications and procedures will be summarized for Weeks 0-52 using the safety population.

### **10.1. Concomitant Medications**

The ATC coding scheme of the WHODD will be used to group medications into relevant categories. Concomitant medications will be summarized by ATC2 level and standardized medication name, with ATC2 levels and standardized medication names within each ATC2 level sorted in descending order of frequency.

### **10.2. Concomitant Procedures**

Concomitant procedures are defined similarly to concomitant medications. Concomitant procedures will be coded according to the MedDRA, and summarized by SOC and PT, with SOCs sorted in alphabetical order and PTs within each SOC in descending order of frequency.

## 11. EFFICACY ANALYSIS

All efficacy analysis tables will be presented by GED-0301 treatment regimen, placebo, and a total group combining all 3 GED-0301 treatment regimens. The 3 GED-0301 treatment regimens will be labeled as GED 160/GED 160 4 WK ALT, GED 160/GED 40 4 WK ALT, and GED 160/GED 40, and the total group combining all 3 GED-0301 treatment regimens will be labeled as GED Total. Formal treatment comparisons will be made between GED Total (ie, GED 160) and placebo for the efficacy analyses of the first 12 weeks, and between each of the 3 GED-0301 treatment regimens and placebo for the efficacy analyses beyond Week 12.

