#### 9.6. Efficacy Analysis

For the efficacy analyses of the first 12 weeks of the study, the three GED-0301 treatment groups will be pooled, due to the same treatment of GED-0301 160 mg QD received during the first 12 weeks, and the treatment comparisons will be made between GED-0301 160 mg QD and placebo. For the efficacy analyses beyond Week 12, the treatment comparisons will be made between each of the three GED-0301 treatment groups and placebo.

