### 9.6.2. Multiplicity

Formal statistical tests are planned for the primary and secondary efficacy endpoints. In order to control the family-wise Type I error rate at the 0.05 level, formal statistical tests will be carried out using a gatekeeping closed testing procedure; details of this procedure, including the endpoints subjected to this procedure and their hierarchy, will be specified in the SAP.

For formal statistical tests that are planned but not performed as a result of the multiplicity adjustment procedure, as well as for any other comparisons that are not subjected to multiplicity adjustment, nominal 2-sided p-values (without adjustment for multiplicity) will be provided as a measure of the strength of association between the endpoint and the treatment effect rather than formal tests of hypotheses.

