### 11.1. Multiplicity

The protocol specifies that a gatekeeping closed testing procedure will be used to control the family-wise Type I error rate at the 2-sided significance level of 0.05 for the primary and secondary efficacy endpoints. Due to the early termination of the study, however, no multiplicity adjustment will be performed.

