## 11.4. Analyses of Secondary Efficacy Endpoints

### 11.4.1. Primary Analyses of Secondary Efficacy Endpoints

The primary analysis of each secondary efficacy endpoint will be performed similarly to the primary analysis of the primary endpoint. The treatment comparisons will be made between GED 160 (combining all 3 GED-0301 treatment regimens) and placebo for the endpoints at Weeks 4 and 12 and between each of the 3 GED-0301 treatment regimens and placebo for the endpoints at Week 52.

The analysis of the proportion of subjects who achieve corticosteroid-free clinical remission at Week 52 among subjects receiving oral corticosteroids at baseline will be based on the subjects included in the ITT population who receive oral corticosteroids for CD at baseline.

[REDACTED]

[REDACTED]

[REDACTED]

[REDACTED]

[REDACTED]

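### Does the SAP give unadjusted comparisons the standing of formal tests, against the protocol's own rule?

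*SAP*

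**What the plan says.** SAP Section 11 first lists the columns of every efficacy table: the three regimens, placebo and a combined GED-0301 group. It then says which pairs are compared: "Formal treatment comparisons will be made between GED Total (ie, GED 160) and placebo for the efficacy analyses of the first 12 weeks". For the later period the same sentence goes on with the words "and between each of the 3 GED-0301 treatment regimens and placebo for the efficacy analyses beyond Week 12".

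SAP Section 11.1, which follows directly, recalls the protocol's gatekeeping procedure and withdraws it: "Due to the early termination of the study, however, no multiplicity adjustment will be performed". SAP Section 16 lists this among the changes from the protocol.

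Protocol Section 9.6.2 plans formal tests for the primary and secondary efficacy endpoints, carried out through a gatekeeping closed procedure with family-wise error held at 0.05. It then sets a fallback. For planned tests that the procedure does not reach, and for "any other comparisons that are not subjected to multiplicity adjustment, nominal 2-sided p-values (without adjustment for multiplicity) will be provided", the p-values serve "as a measure of the strength of association between the endpoint and the treatment effect rather than formal tests of hypotheses".

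The matching sentence in Protocol Section 9.6 has no such adjective; after Week 12 "the treatment comparisons will be made between each of the three GED-0301 treatment groups and placebo". SAP Section 11.4.1 also speaks simply of treatment comparisons, for the combined group "and placebo for the endpoints at Weeks 4 and 12" and for each regimen at Week 52. SAP Section 5.1 adds only that "Confidence intervals (CIs) will be presented as 2-sided 95% CIs".

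**The concern.** Read side by side, the documents seem to conflict. The protocol ties the word *formal* to error-controlled testing and gives everything else nominal status. The SAP removes the error control but calls both the pooled comparison and the three regimen-level comparisons formal. No visible SAP text labels the p-values nominal or descriptive.

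What could be at stake is reporting. If one of the three regimens reached p<0.05 on a single Week 52 endpoint, an author could cite SAP Section 11 and present it as a formal finding although no family-wise control covers it. With five Week 52 secondary efficacy endpoints and three regimens, there are 5 × 3 = 15 opportunities. The two Week 12 secondary efficacy endpoints bring the visible count to 17, and SAP Section 11.4.1 mentions Week 4 as well.

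**Working it through.** **The plan's own figures.** SAP Table 5 gives power at 2-sided 0.05 with no multiplicity adjustment. For proportions p1 (placebo, n1) and p2 (active, n2), with pooled proportion p̄:

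power = Φ{[(p2 − p1) − 1.96·SE0] / SE1}, where SE0 = √[p̄(1 − p̄)(1/n1 + 1/n2)] and SE1 = √[p1(1 − p1)/n1 + p2(1 − p2)/n2].

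| Endpoint | p1, p2 | n1, n2 | SE0 | SE1 | z | Power | Stated |
|---|---|---|---|---|---|---|---|
| Remission, Week 12 | 0.22, 0.36 | 266, 798 | 0.03316 | 0.03056 | 2.455 | 99.3% | 99% |
| Remission, Week 52 | 0.22, 0.36 | 266, 266 | 0.03935 | 0.03888 | 1.618 | 94.7% | 95% |
| ER-50, Week 52 | 0.10, 0.20 | 266, 266 | 0.03096 | 0.03066 | 1.282 | 90.0% | 90% |

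All three reproduce. They were computed without adjustment, so neither dropping the adjustment nor changing a label moves them.

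**What the word does in its paragraph.** Each efficacy table shows four active columns: three regimens and the combined group. SAP Section 11 allows one comparison with placebo through Week 12 (combined group) and three afterwards (each regimen). The other columns are displayed only. The visible text on the primary endpoint analysis, just before SAP Section 11.4, works this way: within-group proportions are given for every group, but the difference, interval and CMH p-value are given only for GED 160 against placebo. A reading of *formal* as marking the compared pairs fits the layout exactly.

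**Whether the nominal rule still applies.**

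1. Protocol Section 9.6.2: a comparison not subjected to multiplicity adjustment gets a nominal p-value.
2. SAP Section 11.1: no comparison is subjected to multiplicity adjustment.
3. SAP Section 16: the visible list of changes removes the gatekeeping procedure and does not mention the nominal rule.

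From 1 to 3, the secondary and regimen-level p-values are nominal whether or not the SAP repeats it.

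**Scale of reading three regimens at 0.05 each.** With equal arms and one shared placebo arm, any two of the three z statistics have correlation 0.5. Under the null:

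- any p<0.05: 1 − ∫φ(u)[Φ(1.96√2 − u) − Φ(−1.96√2 − u)]³du = 0.1254
- any p<0.05 favouring GED-0301: 1 − ∫φ(u)[Φ(1.96√2 − u)]³du = 0.0627
- if the three tests were independent: 1 − 0.95³ = 0.1426

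A single test gives 0.05 and 0.025. These probabilities are the same with or without the adjective, because the same three p-values are computed either way.

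**The case for a change.** The strongest case for acting is that the word is deliberate and cheap to remove. The parallel sentences in Protocol Section 9.6 and SAP Sections 4.4 and 11.4.1 do without it, and Protocol Section 9.6.2 uses it for error-controlled testing, so a reader of both documents may take it in that sense. If it only marks the compared pairs, deleting it loses nothing. A trial stopped early on a Data Monitoring Committee recommendation is also one where a lone regimen-level p<0.05 might be over-read.

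Some of this stands: the wording is loose, and *treatment comparisons* alone would have been cleaner. The rest is weaker. Protocol Section 9.6.2 opens by applying the same adjective to the primary and secondary efficacy endpoints, so the SAP may simply carry the term over. The feared misreading requires skipping the next SAP section, which says no adjustment is made, and the protocol rule that fixes the consequence. The visible SAP sets no significance threshold or success rule that the label would trigger.

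The lack of a visible nominal label is not good evidence of a gap either. SAP Sections 5.1, 11 and 16 all carry redactions, including entries in the list of changes due to early termination.

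Counting all 17 visible secondary comparisons would give a larger error figure, but it would need response rates and correlations that the documents do not supply. It would also measure the declared loss of gatekeeping, not the effect of this word.

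**Conclusion.** This is a clerical looseness with no gain from a change. The comparisons in SAP Section 11 are unadjusted, SAP Sections 11.1 and 16 say so, and Protocol Section 9.6.2 already makes their p-values nominal. An analyst following both documents produces the same tables and should describe the secondary and regimen-level results as descriptive. The effect of the word on any estimate, p-value, sample size or power is zero.

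The 12.5% figure (6.3% favouring GED-0301) describes what unadjusted reading of one Week 52 endpoint costs, assuming equal arms, a shared placebo and a global null. The primary Week 12 analysis is one pooled comparison and is not inflated by the others.

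The conclusion rests on the protocol's nominal rule remaining in force, which nothing visible contradicts. A redacted nominal statement would only reinforce it. Visible or redacted SAP text that attached a claim of significance to the regimen-level comparisons would change the assessment; no visible text does.
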